7.6 Follow-up Procedures

Subjects will be evaluated prior to discharge, 30 days post-procedure, 180 days post-procedure, and 365 days post-procedure. All follow-up visit dates will be calculated based on a 30-day calendar.

7.6.1 Discharge Visit

The subject may be discharged when clinically stable, at the discretion of the investigator.

7.6.2 30 Day Visit (\pm 14 days)

All study sites will be asked to collect follow-up data per each subject at 30 days post-procedure. Study reported evaluations are not required except for the quality of life questionnaire; otherwise all data collected will be per standard of care. A typical follow-up visit may include blood tests, imaging, physical exam, review of concomitant medications and any device related adverse events.

7.6.3 180 Day Visit (\pm 30 days)

All study sites will be asked to collect follow-up data for each subject at 180 days post-procedure, per site standard of care. Study reported evaluations are not required except for the quality of life questionnaire; otherwise all data collected will be per standard of care. A typical follow-up visit may include blood tests, imaging, physical exam, review of concomitant medications and any device related adverse events.

7.6.4 365 Day Visit (\pm 60 days)

All study sites will be asked to collect follow-up data via telephone or visit for each subject at 365 days post-procedure. If a clinic visit is standard of care at 365 days, data from the visit will be collected. If a clinic visit is not standard of care, follow-up information for this visit will be collected via telephone. This 365-day visit will conclude the subject's participation in the study.

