Primary Study Evaluations	
1. Procedural success defined as completing the planned procedure without femoral access bailout2. Technical success defined as delivery of HydroPearl to the target vessel and slowing the blood flow with microsphere embolization.3. Freedom from Major Adverse Events within 30 days of procedure, defined as:
a. Deathb. MIc. Stroke4. Freedom from radial access related complications at 30 days, defined as:
a. Radial artery occlusion (reverse Barbeau and/or Ultrasound, per site standard of care)b. Hand ischemiac. Arteriovenous fistulad. Pseudoaneurysme. Any complication requiring surgical and/or endovascular intervention within 30 days of index procedure
Additional Evaluations	
1. Incidence of Radial Artery Occlusion Complications at any time
a. Arteritis

	
b. Cellulitisc. Ecchymosisd. Pain at puncture sitee. Hematoma 
2. Quality of Life and Health Economics3. Procedural endpoints:
a. Blood lossb. Patient radiation exposurec. Contrast volumed. Time to hemostasise. Total procedural timef. Time to dischargeg. Operative timeh. Radial cocktail components and frequency of administration4. Access endpoints:
a. Radial artery spasmb. Time to dischargec. Radial access pain VAS5. Closure endpoints
a. Time to hemostasisb. Time to ambulation
Procedure Evaluations	
1. Tumor type2. Number and size of tumors / fibroids3. Post embolization syndrome4. UFE:
a. If post-op MRI is obtained per standard of care: Effectiveness of HydroPearl measured by MRI.
i. Infarction is characterized by complete (100%), 90-99%, 50-89%, or less than 50%.ii. Uterine Volumeiii. Dominant Fibroid Volumeb. EQ-5Dc. UFS-QoLd. Return to normal activitiese. Pain VASf. Symptoms including bleeding and bulkg. Pregnancy intention and occurrence5. Prostate Artery Embolization:
a. IPSS with Quality of Lifeb. EQ-5Dc. Return to normal activitiesd. Pain VAS

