Further studies of TRA for PCI have consistently demonstrated its benefits as compared to femoral access, including decreased bleeding, access site complications and post-procedure recovery time, and increased patient satisfaction and cost effectiveness. (Rao, Cohen, Kandzari, Bertrand, & Gilchrist, 2010) . Limitations to the transradial approach have been recognized, such as a learning curve which must be overcome by new operators, limitations of available equipment suitable for radial use, and relatively rare complications such as localized access site hematoma. Radial artery occlusion is reportedly rare and upon occurrence is often asymptomatic due to collateral perfusion supplied by the ulnar artery. (Fischman, Swinburne, & Patel, 2015).

The benefits of transradial access are considered by many physicians to outweigh these drawbacks, leading to the steady uptake of TRA for PCI; an estimated 16% of PCI procedures in the US were conducted transradially in the year 2012, up from 1.2% in 2007. Within the previous decade, additional support for TR-PCI has been generated by multiple prospective, randomized trials, including the RIFLE, RIVAL and MATRIX trials which have consistently demonstrated decreased access site bleeding and net adverse events.

(Fischman, Swinburne, & Patel, 2015). The expanding body of evidence favoring transradial access for PCI prompted physicians to branch beyond the coronary space to transradial access for visceral and peripheral arterial interventions, (Rao, Cohen, Kandzari, Bertrand, & Gilchrist, 2010) and more recently, for interventional radiology procedures, such as embolization of hypervascular tumors, including uterine fibroids and liver tumors ((Yamada, et al., 2018)).

Uterine fibroid embolization, traditionally achieved via femoral access, is considered by the American College of Obstetrics and Gynecology as a safe, minimally invasive primary treatment for symptomatic uterine fibroids. (Keung, Spies, & Caridi, 2018) . The first reported series of UFE achieved via radial access dates to 2014, where Resnick, et al. (2014) conducted UFE on 29 patients at a single institution with a 100% success rate. No immediate major or minor complications were observed in any patients, and radial artery patency was evident in all patients at one month follow up. (Resnick, et al., 2014). Recently,

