Gjoreski, et al. (2019) directly compared the safety and feasibility of UFE when achieved through radial as opposed to femoral access. In this retrospective study, 13 femoral procedures and 11 transradial procedures all yielded a 100% success rate with no significant difference in access site related and overall adverse events noted between cohorts. Procedure and fluoroscopy times were reportedly shorter in the radial group; a mean procedure time of 60.3 minutes was associated with the radial group as compared to 72.4 minutes in the femoral cohort, and mean fluoroscopy time was 21.1 minutes and 25.3 minutes in the radial and femoral cohorts, respectively. (Gjoreski, Gjoreski, & Nancheva, 2019).

The development of transradial access for embolization of hepatic tumors can be traced back to a 2003 report by Shiozawa et al. (2003) which described transcatheter arterial chemoembolization (TACE) in 327 patients, 177 of which were accessed radially and 150 via femoral access. Therapeutic efficiency was observed in both cohorts, with a lower complication rate in the radial cohort (4.6%) compared to the femoral (12.7%). (Shiozawa, et al., 2003). In addition to chemoembolization, radial access has also been utilized for radioembolization of hepatic tumors. A study by Fischman, et al. published in 2016 described 30 procedures conducted in 26 patients which supported the safety and tolerability of TRA for hepatic artery embolization. In this study, 14 TACE procedures, 14 Y90 procedures and 2 bland embolization procedures yielded a 100% technical success rate with no major AEs reported at one month follow up. (Fischman, et al., 2013) . In a 318 patient study, a total of 329 planning angiograms and 245 Y90 embolization procedures resulted in technical success in 97.7% of cases, superficial bruising observed in 2.3% of cases, and a radial artery occlusion rate of 1.6%. (Bishay, et al., 2016) .

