3.2.1 Primary Evaluations

Primary Safety Evaluation:

The primary safety evaluation is freedom from major adverse events and radial access complications within 30 days post-procedure.

Major Adverse Events are defined as:

1. Death
2. MI
3. Stroke

Radial Access related complications are defined as:

1. Radial artery occlusion
2. Hand ischemia
3. Arteriovenous fistula
4. Pseudoaneurysm
5. Any complication requiring surgical and/or endovascular intervention within 30 days of index procedure.

Primary Efficacy Evaluation:

The primary efficacy evaluations are procedural success and technical success.

1. Procedural success is defined as completing the planned procedure without femoral access bailout.
2. Technical success is defined as delivery of HydroPearl to the target vessel and slowing the blood flow with microsphere embolization. Embolization may be confirmed clinically or radiologically at the discretion of the site investigator.

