7.2 Procedure

Subjects that meet the eligibility criteria and have signed the informed consent will have their scheduled procedure performed in accordance with investigator/site standard practices. Any on-label use of HydroPearl microspheres are permitted this study; that is, treatment of arteriovenous malformations and hypervascular tumors including uterine fibroids.

Table 2: Schedule of Events

Assessment	Screening / Baseline	Procedure	Discharge	30 Day Follow-up ±14 days	180 Day Follow-up ±30 days	365 Day Follow-up ±30 days
Informed Consent	X					
Eligibility Criteria	X					
Medical History/Demographics	X					
Pregnancy Test [¶]	X					
Blood Tests, including platelets and INR (if available) *	X	X	X	X	X	X
Embolized target organ Imaging (if available)	X	X	X	X	X	X
Physical Exam	X	X	X	X	X	X
Procedure, Access, Closure Evaluations		X				
Quality of Life questionnaires and return to normal activities	X		X	X	X	X
Concomitant Medications (Intra-op and Anticoagulation / Antiplatelets Only)	X	X	X	X		
Device Related Adverse Events ^{§§}		X	X	X	X	X

[¶] Pregnancy test if female of child-bearing potential (collected prior to procedure according to site standard of care)

* Blood Tests include Complete Blood Count (CBC), Platelet Count, Serum Creatinine, Hemoglobin (HGB), Blood Urea Nitrogen (BUN), Hematocrit (HCT) and Prothrombin time/INR, only as collected per standard of care

^{§§} Device related adverse events should be recorded during the entire course of the study from time of enrollment through end of 180 Day Follow-up visit.

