7.7 Clinical Data Collection

Information about subject demographics, eligibility requirements, procedure, specific concomitant medications as well as complications and/or device related adverse events will be collected on the eCRFs provided by the Sponsor. The eCRFs should accurately reflect data contained in the subject's medical records (i.e. source documents).

8 Adverse Events

Subject complications will be monitored via the reporting of device related adverse events occurring from the time of enrollment (insertion of guidewire into radial artery) through study completion (withdrawal for any reason or completion of 365-day follow-up visit). For this registry, adverse events collected will be limited to any events possibly, probably or definitely related to a Terumo device, as described below in Section 8.2.

Where an adverse event has, by its nature, a prolonged course, the event will be considered a single event and not multiple events.

The investigator is not required to actively seek adverse events from a subject once a subject has exited the study. If the investigator learns of any device related adverse event at

any time after a subject's exit from the study, the investigator should promptly report it to the Sponsor.

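### Radial artery occlusion is a primary safety component, but nothing in the documents describes recording who was tested for it, so its rate may have no known denominator (minor; cheap to improve)

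*Combined protocol and SAP*

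**What the plan says.** Section 3.2.1 states: "The primary safety evaluation is freedom from major adverse events and radial access complications within 30 days post-procedure". RAO is the first access complication on its list, and no method of detection is given there. The synopsis words the access evaluation as "Freedom from radial access related complications at 30 days, defined as" and gives the method as "Radial artery occlusion (reverse Barbeau and/or Ultrasound, per site standard of care". Section 1 says: "Radial artery occlusion is reportedly rare and upon occurrence is often asymptomatic due to collateral perfusion supplied by the ulnar artery".

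For the 30-day visit, Section 7.6.2 says: "Study reported evaluations are not required except for the quality of life questionnaire; otherwise all data collected will be per standard of care". Neither schedule of events has a row for radial patency, and the access evaluations are marked at the procedure only. Table 2 marks a physical exam at 30 days without a stated patency component. Its imaging row reads "Embolized target organ Imaging (if available".

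On data capture, Section 7.7 says that "complications and/or device related adverse events will be collected on the eCRFs provided by the Sponsor", and Section 8 follows complications through reports of device-related events. The synopsis and Section 11 add that imaging results, where imaging is done, go into the eCRF.

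On analysis, Section 13.3 uses all treated subjects, Section 13.4 presents the primary evaluations by site, and Section 13.5 uses observed cases and reports how many data are missing. None of these says how a subject without a patency test is classified for RAO.

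**The concern.** Event reporting delivers positives. It does not by itself separate a patent artery that was tested from one that nobody examined. For an event that produces symptoms this matters little. For one that the protocol itself describes as often silent, the absence of a report says little unless the reader knows whether anyone looked.

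If test status is not recorded, the observed-case rule of Section 13.5 cannot be applied to RAO and the promised missing count cannot be produced for it. Untested subjects then pass into the all-treated set as free of RAO, which pulls the rate down. The by-site presentation would also mix testing habit with safety: a site that never tests would look better than one that always does.

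There is a smaller wording gap beside this. Section 3.2.1 counts complications within 30 days, and the synopsis counts them at 30 days. An occlusion found at discharge in an artery that is patent at the 30-day visit is an event under one wording and arguably not under the other.

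**Working it through.** **Inputs from the documents.** Up to 100 subjects (Section 2.2 and synopsis). Section 1 cites, from one radioembolization series, "a radial artery occlusion rate of 1.6" percent; this is taken as the true rate, p = 0.016.

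**Assumptions.** The share tested, t, and the share of RAO that is silent, s, are not given. I use t = 0.75, 0.50, 0.25 and s = 0.5, with s = 1 as the extreme. All symptomatic RAO is taken to be detected.

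**The plan's own figure.** Section 13.1 claims more than 80% probability of seeing at least one major complication at a 1.6% rate in 100 evaluable patients: 1 − 0.984^100 = 80.1%. It reproduces. Section 13.1 does not say that this rate refers to RAO. Applied to RAO, the figure needs all 100 to be assessed. With 75, 50 or 25 assessed, 1 − 0.984^n gives 70.2%, 55.4% and 33.2%.

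**Untested subjects counted as RAO-free.** Reported rate = p × [(1 − s) + s × t].

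| Share tested | s = 0.5 | s = 1 |
|---|---|---|
| 75% | 0.016 × 0.875 = 1.4% | 1.2% |
| 50% | 0.016 × 0.750 = 1.2% | 0.8% |
| 25% | 0.016 × 0.625 = 1.0% | 0.4% |

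**Untested subjects dropped.** If testing is unrelated to RAO, the expected rate among those tested stays 1.6%; only precision is lost. If symptomatic cases always enter and everyone else enters with probability t, the rate is p(0.5 + 0.5t) / [p(0.5 + 0.5t) + 0.984t]:

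- t = 0.75: 0.014 / (0.014 + 0.738) = 1.9%
- t = 0.50: 0.012 / (0.012 + 0.492) = 2.4%
- t = 0.25: 0.010 / (0.010 + 0.246) = 3.9%

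The direction is not fixed. Testing after difficult access, or concentrated at sites with more RAO, would also push the rate up. Testing concentrated at sites with less RAO would push it down.

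**Against sampling error.** About 100 × 0.016 = 1.6 occlusions are expected. One event in 100 is 1.0%, exact 95% interval 0.03% to 5.4%. One in 50 is 2.0%, interval 0.05% to 10.6%. At 50% tested and half silent, the shift is 0.4 points down (1.6% to 1.2%) or 0.8 points up (1.6% to 2.4%), well inside either interval.

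**The case against.** The strongest reply is that this is an observational registry of on-label use, and that leaving RAO testing to site practice is deliberate and stated. That stands. A reader might infer that the plan is defective because it mandates no 30-day patency test; the documents do not support that reading, and nothing here asks for one.

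Second, Section 13.5 already uses observed cases and counts the missing. Read with the synopsis wording on how RAO is tested, this leans towards treating an untested subject as missing. But the plan does not say so, and the rule works only if test status is recorded.

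Third, the record may be fuller than the event-reporting text suggests. The synopsis schedule has an imaging row with no organ limit at discharge and 30 days, and imaging results are to be entered when imaging is done. A normal radial ultrasound might be captured that way, although Table 2 narrows the row to the embolized organ. A reverse Barbeau test is not imaging, so the gap is clearest there. The eCRF itself is not among the documents and may hold a patency field; one cannot infer that test status goes unrecorded, only that no section describes recording it.

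Fourth, the effect is small, which also stands.

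**Conclusion.** The point holds as a minor one about what the reported RAO rate means. If the eCRF has no patency field, untested subjects in effect count as free of RAO. With a true rate of 1.6% and half of occlusions silent, the reported figure would be 1.4%, 1.2% or 1.0% at 75%, 50% or 25% tested. The tested and silent shares are assumptions, and the true rate is borrowed from one cited series.

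Two further inferences go too far. One is that the safety conclusion is invalid: the shifts are smaller than the sampling error of 100 subjects, and Section 13.7 plans no hypothesis test. The other is that dropping untested subjects repairs the rate, or always inflates it: that is unbiased only if testing is unrelated to RAO risk, and otherwise the bias can go either way.

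It is still worth acting on. Section 13.7 defines study success by enrollment with few missing data and sound descriptive statistics, and test status is hard to recover reliably once data collection is over.

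**What to change.** 1. Unless the eCRF already has it, add one item at discharge and at 30 days: radial patency assessed yes/no, method, date, result. Testing stays per site standard of care.
2. In Sections 13.5 and 13.7, state that a subject with no patency assessment and no clinically detected RAO is missing for the RAO component. Report the number assessed, overall and by site. Give RAO among subjects assessed or with clinically detected RAO, and beside it RAO over all treated subjects, labelled as a lower figure. Neither should stand alone: at 50% tested and half silent, with other subjects tested without regard to RAO, the pair would be 2.4% and 1.2% around a true 1.6%.
3. Where the combined evaluation of Section 3.2.1 is reported, give events over all treated subjects, labelled as a lower figure for the RAO part, with the number not assessed. Do not drop event-free untested subjects from it: every event would stay while event-free subjects left, so inclusion would depend on outcome.
4. Reconcile the 30-day wording of Section 3.2.1 with that of the synopsis, and say how an occlusion found at discharge but patent at the 30-day visit is counted.

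The cost is at most one eCRF item and a few lines of text, with no added test or visit. The price in reporting is two RAO figures instead of one, and a smaller denominator and wider interval for the assessed-subject figure. If the eCRF already holds the field, only the wording in items 2 to 4 is needed.

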8.3 Follow-up of Adverse Events

All device related adverse events observed from the time of enrollment throughout the duration of the study must be reported on the eCRF. All device related adverse events will be followed until resolution or stabilization of symptoms through study completion and/or the subject withdraws consent. Resolution means that the subject has returned to a baseline state of health. Stabilization means that the investigator does not expect any further improvement or worsening of the adverse event.

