13.5 Handling of Missing Data

All data will be collected when possible to limit the amount of missing data. Site study coordinators will work with the site principal investigator to collect accurate patient data. The number of missing data will be reported. Only observed cases will be considered.

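### Primary safety is scored at 30 days, but Section 7.6.2 requires only the quality of life questionnaire there, conflicts with the schedules of events, and names no route for ascertaining the safety components when no clinic visit is routine

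*Combined protocol and SAP*

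**What the plan says.** Section 3.2.1 sets the endpoint and its horizon: "The primary safety evaluation is freedom from major adverse events and radial access complications within 30 days post-procedure". Its components are death, MI and stroke, and five kinds of radial access complication. The synopsis gives the method for the first of these: "Radial artery occlusion (reverse Barbeau and/or Ultrasound, per site standard of care".

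Section 7.6.2, on the 30-day visit, opens with a general request: "All study sites will be asked to collect follow-up data per each subject at 30 days post-procedure". It then limits what is obligatory: "Study reported evaluations are not required except for the quality of life questionnaire; otherwise all data collected will be per standard of care". Adverse events appear only among the things that a typical visit may include.

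Section 7.6.4, on the 365-day visit, is the only place that deals with subjects who have no routine clinic visit: "If a clinic visit is not standard of care, follow-up information for this visit will be collected via telephone".

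Other text points towards a real 30-day assessment. Section 7.6 states: "Subjects will be evaluated prior to discharge, 30 days post-procedure, 180 days post-procedure, and 365 days post-procedure". Section 9.1 foresees visits at which the investigator or a designee reviews the subject's status. The synopsis schedule and Table 2 both mark physical exam and device-related adverse events at 30 days. In both, the blood test and imaging rows are qualified as applying only where available, and the physical exam row is not. Section 8.3 adds: "All device related adverse events observed from the time of enrollment throughout the duration of the study must be reported on the eCRF". Section 8 confines adverse event collection to events at least possibly related to a Terumo device.

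For missing outcomes, Section 13.5 says that their number will be reported and then: "Only observed cases will be considered".

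**The concern.** To score primary safety, each subject's status on every component must be known through day 30. Under Section 7.6.2, a site with no routine 30-day clinic visit meets the protocol once the questionnaire is returned. The adverse event rules do not close the gap. They oblige a site to report device-related events that it observes, but not to look for events, and they leave out a stroke or MI judged unrelated to a Terumo device.

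Such a subject may then be unscored and dropped, which shrinks the denominator of the main safety result. Which subjects drop out would follow site practice, so the result would partly reflect which sites see patients at a month. The poolability analysis in Section 13.4 could pick up those differences as site effects. If silence were instead read as no event, the freedom-from-event rate would be biased upward (equivalently, the complication rate downward), and no missing data would show.

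The plan itself treats completeness as the goal: Section 13.7 defines study success as full enrolment with little missing data.

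**Working it through.** **What is required at day 30, set side by side**

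| Item | Expected by | Required by |
|---|---|---|
| Some contact | 7.6, 7.6.2, 9.1, both schedules | 7.6.2, through the questionnaire |
| Physical exam | both schedules, unqualified | not required under 7.6.2 |
| Device-related adverse events | both schedules | 8.3, if observed |
| Death, MI, stroke regardless of device | 3.2.1, as endpoint | no passage |
| Radial patency check | synopsis, per site practice | no passage |
| Telephone if no routine visit | – | 7.6.4, at 365 days only |

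The physical exam row is a direct conflict between Table 2 and Section 7.6.2. The last three rows are the gap.

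**Inputs for the size**
- n = 100 evaluable subjects and a major complication rate of 1.6% (Section 13.1)
- Enrolment ceiling of 100 (Section 4.2)
- Number unscored: not in the documents. Assumed to be 1, 10 or 20. A fourth case of 30 is what would arise if one site at the 30% cap in Section 2.2 had no scored subjects.

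**The plan's own figure.** P(at least one event) = 1 − (1 − 0.016)^n. At n = 100 this is 1 − 0.984^100 = 0.8007, which reproduces the stated figure of more than 80%. It is also the smallest n that does so, since 1 − 0.984^99 = 0.797.

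**Effect of unscored subjects.** The second column uses the formula above. The third is the exact two-sided 95% upper limit on the event rate with zero events, 1 − 0.025^(1/n).

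| Scored n | P(at least one event) | Upper limit, 0 events |
|---|---|---|
| 100 | 80.1% | 3.6% |
| 99 | 79.7% | 3.7% |
| 90 | 76.6% | 4.0% |
| 80 | 72.5% | 4.5% |
| 70 | 67.7% | 5.1% |

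Keeping 100 evaluable subjects would need 100/0.90 = 111.1, so 112 enrolled, at 10% unscored, or 100/0.80 = 125 at 20%. Both exceed the ceiling.

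**Direction of bias.** Suppose 2 events are seen among 80 scored of 100 (an illustration). Observed cases give freedom of 78/80 = 97.5%. Reading the 20 silent subjects as event-free gives 98/100 = 98.0%, which is the highest value possible. The lowest is 78/100 = 78%, which would need every unscored subject to have had an event. It is a logical bound and not a forecast.

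**The case against.** Follow-up by standard of care is a deliberate feature of a post-market registry, and the study tests no hypothesis. Several passages expect a 30-day evaluation, the questionnaire means that each subject must be reached, and Section 7.7 says that complications will be collected on the eCRFs. Adverse event reporting runs to the 365-day contact, so a dated event from the first month can still surface later. Deaths are partly protected, because Section 13.2.1 uses the date of death in computing time in study. All of this stands.

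A reader might therefore be tempted by three stronger readings, none of which the documents support.
- *That no safety contact is planned at 30 days.* The passages above say otherwise. What is missing is its required content.
- *That silent subjects will be counted as event-free.* No passage says so, and the eCRF is not among the documents. It is a risk left open by the plan, not a stated rule.
- *That the telephone route was withheld at 30 days.* Section 7.6.4 can equally be read as relaxing an expected visit at one year. The asymmetry matters only because Section 7.6.2 does not make the 30-day visit obligatory.

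Nor do the documents show that routine 30-day visits differ by indication or country.

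The objection does not supply a duty to ascertain the components. Later contacts cannot repair this for radial artery occlusion, which the Background describes as often without symptoms, so it could not reliably be dated to the first 30 days.

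**Conclusion.** The point holds as a gap in ascertainment together with an internal conflict. A 30-day contact is expected, but Section 7.6.2 requires nothing at it that would score primary safety, and it contradicts the schedules on the physical exam.

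The size depends on an unscored share that the documents do not give. Over an assumed 1 to 20 unscored of 100, the Section 13.1 probability falls from 80.1% to between 79.7% and 72.5%. With 10 or 20 unscored, the zero-event upper limit rises from 3.6% to 4.0% or 4.5%. The loss is modest at the low end, but Section 13.1 has no slack: a single unscored subject takes it below 80%. The 1.6% rate there is for major complications and not for the whole composite, so these figures measure lost information rather than the precision of the composite itself. The stated probability is correct as computed; it relies on every enrolled subject being evaluable.

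The study is descriptive, so this is an improvement that should be made and not a fatal flaw.

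**What to change.** 1. In Section 7.6.2, state that where a clinic visit is not standard of care at 30 days, follow-up information is collected by telephone.
2. Make status since the procedure a required eCRF entry for death, MI, stroke and each listed access complication: yes, no or unknown, with the date and mode of contact. Record death, MI and stroke whatever their relation to a Terumo device, and say in Section 8 that these items fall outside its device-related limit.
3. Record radial artery occlusion as unknown unless it was assessed by reverse Barbeau or ultrasound, and report the number assessed. A negative answer by telephone cannot exclude it.
4. In Section 13, score a component as event-free only on an explicit no, and report the denominator for each component.
5. Reconcile Section 7.6.2 with Table 2 and the synopsis schedule, in particular on the physical exam.

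The cost is a protocol amendment of a few sentences, one short form, and a few extra questions at a contact already needed for the questionnaire. One limit remains: occlusion stays unscored in subjects followed only by telephone, so the composite cannot be fully scored for them. The change makes that number visible but does not remove it.
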